## **8.4 Reporting of SAEs and Unanticipated Events**

### **8.4.1 Investigator reporting: Notifying the REB**

Serious adverse events and unanticipated events should be recorded and reported to the REB in accordance with local reporting requirements and timelines.

### **8.4.2 Investigator reporting: Notifying the Sponsor**

The investigator is responsible for reporting serious adverse events to the sponsor in accordance with applicable regulations and reporting requirements and timelines.

Reporting should include a description of the event in sufficient detail to allow for a complete medical assessment of the case and independent determination of possible causality. The minimum information required includes at least one identifiable participant, one identifiable reporter, one serious reaction, and one suspect product.

### **8.4.3 Investigator Reporting of SUADRs: Notifying Health Canada**

In the event of an incident related to a failure of the device or deterioration in its effectiveness, or any inadequacy in its labelling or in its directions for use that leads to the death or a serious deterioration in the state of health of a patient, user or other person, or could do so were it to recur, the qualified investigator of this study will report the incident to Health Canada. The qualified investigator will report the incident and the circumstances surrounding it to the Minister and to the manufacturer or importer of the device within 72 hours after it comes to the attention of the qualified investigator.

### **8.4.4 Manufacturer or Importer Reporting of SUADRs: Notifying Health Canada**

The manufacturer of the investigational device is required to report medical device incidents to Health Canada. A preliminary report will be submitted to the Minister within 10 days after the manufacturer becomes aware of an incident, if the incident has led to the death or a serious deterioration in the state of health of a patient, user or other person, or within 30 days after the manufacturer becomes aware of an incident, if the incident has not led to the death or a serious deterioration in the state of health of a patient, user or other person, but could do so were it to recur. The preliminary report will include:

(a) the name of the device and its identifier, including the identifier of any medical device that is part of a system, test kit, medical device group, medical device family or medical device group family;

- (b) the manufacturer, the name and address of that manufacturer and of any known importer, and the name, title and telephone and facsimile numbers of a representative of the manufacturer to contact for any information concerning the incident;
- (c) the date on which the incident came to the attention of the manufacturer;
- (d) the details known in respect of the incident, including the date on which the incident occurred and the consequences for the patient, user or other person;
- (e) the name, address and telephone number, if known, of the person who reported the incident to the manufacturer;
- (f) the identity of any other medical devices or accessories involved in the incident, if known;
- (g) the manufacturer's preliminary comments with respect to the incident;
- (h) the course of action, including an investigation, that the manufacturer proposes to follow in respect of the incident and a timetable for carrying out any proposed action and for submitting a final report; and
- (i) a statement indicating whether a previous report has been made to the Minister with respect to the device and, if so, the date of the report.

After the preliminary report is made, a final report shall be submitted to the Minister, containing the following:

- (a) a description of the incident, including the number of persons who have experienced a serious deterioration in the state of their health or who have died;
- (b) a detailed explanation of the cause of the incident and a justification for the actions taken in respect of the incident; and
- (c) any actions taken as a result of the investigation, which may include
  - (i) increased post-market surveillance of the device,
  - (ii) corrective and preventive action respecting the design and manufacture of the device, and
  - (iii) recall of the device.

#### **8.4.5 Events of Special Interest**

The regulatory sponsor is responsible for distributing blinded expedited reports of serious adverse events and unanticipated events to each investigator for submission to local Ethics Committees within 15 days of sponsor awareness.

### **8.5 Type and Duration of Follow-up for Adverse Events**

AEs occurring as of the first contact of the investigational product and 7 days following removal of the investigational product will be collected. AEs recorded during this period will be followed through to resolution, or until the event is assessed as chronic or stable. If an AE remains unresolved at the conclusion of participation, the Investigator will make a clinical assessment to determine whether continued follow-up of the AE is warranted.

## **8.6 Reporting and Entry Timelines**

Study investigators will report SAEs to the sponsor within the following timelines:

- All deaths and immediately life-threatening events, whether related or unrelated, will be recorded and reported to the sponsor within 24 hours of site awareness.
- Serious adverse events other than death and immediately life-threatening events, regardless of relationship, will be reported to the sponsor within 72 hours of site awareness.

Adverse event information will be entered into the CRF in a timely manner and **no later than 15 days** from the time the investigator becomes aware of the event.

Serious adverse event information will be entered into the CRF in a timely manner/**within 72 hours** from the time the investigator becomes aware of the event.

## **9 SITE MONITORING, AUDITING AND INSPECTING**

### **9.1 Site Monitoring Plan**

Site monitoring is conducted to ensure the safety of human study participants and the protection of their rights and well-being. Monitoring also verifies that collected study data is accurate, complete and verifiable by source documentation and that the study is conducted in accordance with the protocol and operating procedures.

The majority of Clinical Monitoring in this study will be done remotely by comparing completed Case Report Form (CRF) data to de-identified source documentation which will be made available for Clinical Monitor review. If needed, each site may be visited by a Clinical Monitor during the study to verify data entry and regulatory documentation. On-site monitoring visits will be conducted according to the applicable ICH-GCP guidelines to ensure protocol adherence, quality of data, compliance with regulatory requirements and continued adequacy of the investigational site and its facilities. The Investigator will cooperate in the monitoring process by ensuring the availability of the CRFs, source documents and other necessary documents via remote source document upload during the course of the study, as well as at the time of any on-site monitoring visits. The Investigator will also ensure prompt attention to any matters brought to his/her attention by the Clinical Monitor.

Study data will be entered in the CRF by trained site study personnel. Data validation edit checks will be defined and implemented. Inconsistent and questionable data detected during the data entry or data validation process will be queried. Data clarification forms (DCF) will be generated and any discrepancies will be resolved.

### **9.2 Auditing and Inspecting**

The investigator will provide direct access to source data/documents for the purposes of study-related monitoring, audits, and inspections by the REB, the sponsor, and applicable regulatory bodies. The investigator will permit the review of all study related documents (e.g. source documents, regulatory documents, data collection instruments, study data etc.) and will ensure access to applicable study-related facilities (e.g. pharmacy, diagnostic laboratory, etc.).

## **10 STATISTICAL CONSIDERATIONS**

### **10.1 Study Hypotheses**

We hypothesize that participants with sleep apnea will have a greater 12-month change in their Montreal Cognitive Assessment scores than those without

### **10.2 Sample Size Considerations**

We anticipate that ~30% of participants (i.e. 210 participants) will have sleep apnea. Based on this, we estimate 86% power to detect a ~0.5 point difference in 12-month change in MoCA between participants with and without sleep apnea. As it is possible that treatment of sleep apnea may be a potential source of noise regarding longitudinal cognitive outcomes, we will adjust for this statistically by collecting information on treatment and adjusting as a covariate.

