	
informed consent and then prepare shipment of ANNE Vital Sign System and instructions to participant. After study device and associated materials are shipped to and received by the participant, study staff will instruct the participant on the proper application and use of the ANNE Vital Sign System over remote video-conference according to manufacturer recommendations. Participants will wear the sensors for 24 hours and this procedure will be completed at the Baseline visit and repeated at the Month 12 visit.

Statistical Analysis:
	
Cardiopulmonary data – .shrd file type – from the ANNE Vital Sign System will be downloaded locally by Sunnybrook Research Institute (SRI) who will convert to .edf file type, and manually annotate to extract information on sleep apnea. SRI will then upload de-identified, processed data to the Longitudinal Online Research and Imaging System120 (LORIS). All uploads and downloads will be by Secure File Transfer Protocol (SFTP). We will quantify the apnea hypopnea index (AHI), oxygen desaturation index (ODI), hypoxemia burden, and time with oxygen saturation below 90% (O2<90). Participants will be considered to have sleep apnea if their AHI is greater than or equal to 15. We will relate presence of sleep apnea to 1-year change in cognition measured using the Montreal Cognitive Assessment (MoCA), collected as part of CTU and affiliated trials. Sex-stratification will be used in analyses as appropriate.

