### **3 STUDY OBJECTIVES**

#### **3.1 Primary Objective**

The primary objective of this study is to test the hypothesis that sleep apnea is associated with accelerated cognitive decline in older adults at risk for dementia. We will measure sleep apnea at baseline and 12 months later and relate this to cognitive function at the same time points.

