## 4 STUDY DESIGN

### 4.1 General Design

The Canadian Therapeutic Platform Trial for Multidomain Interventions to Prevent Dementia (CTU) is a Canada-wide study of older adults at risk for dementia, undertaken by the Canadian Consortium on Neurodegeneration that will begin recruitment in May 2022 and is anticipated to recruit 750 participants from May 2022-April 2024. The main goal of the CTU study is to serve as a shared platform to support studies of technologies and interventions to prevent dementia. These sub-studies are able to share CTU resources for recruitment and outcome ascertainment.

Participants in CTU and affiliated studies will be invited to participate in the ANNE Vital Sign System sub-study. CTU recruiting sites will refer potential participants to Sunnybrook Research Institute (SRI) to obtain informed consent and then prepare shipment of ANNE Vital Sign System and instructions to participant. The informed consent process will be conducted according to sections 7.1 and 13.3 of this protocol. After study equipment and materials are shipped to and received by the participant, study staff will instruct the participant on the proper application and use of the ANNE Vital Sign System over remote video-conference. Specifically, study staff will instruct the participant to affix the ANNE Vital Sign System chest sensor to the participant's chest using electrode paste, the ANNE chest adhesive, and Tegaderm or similar. Study staff may ask participants to shave a 3"x2" section of their chest, but participants will be informed this is optional. Next, study staff will instruct the participant to affix the ANNE Vital Sign System finger sensor to the participant's non-dominant index finger using the ANNE limb adhesive. Participants will wear the sensors for 24 hours before removing it themselves at home and shipping back to Sunnybrook Research Institute using a pre-paid, pre-addressed package. This procedure will be completed at the Baseline visit and repeated 12 months later.

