## **4.2 Primary Outcomes/Endpoint(s)**

We will quantify the apnea hypopnea index (AHI), oxygen desaturation index (ODI), hypoxemia burden, and time with oxygen saturation below 90% ( $O_2 < 90$ ). A participant will be considered to have sleep apnea if their AHI is greater than or equal to 15. In addition, we will quantify 24-hour resting heart rate, and average heart rate, which are important physiological consequences of sleep apnea.

As part of their participation in CTU, participants will undergo a Montreal Cognitive Assessment (MoCA) at baseline and after 12 months. We will relate the presence of sleep apnea to change in MoCA scores between baseline and 12 months using t-tests. We will then use mediation analyses to test if any observed associations are mediated by effects of sleep apnea on average and daytime resting heart rate.

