## **7.3 Study visits/Follow up**

Baseline procedures will be repeated 12 months later. Participants at either time point with an AHI of  $\geq 15$  as determined by our quantification will be called via telephone by study staff to be a) notified that they have a high probability of having sleep apnea and if accompanied by severe sleepiness should refrain from driving, b) encouraged to contact their family physician for clinical evaluation where an official diagnosis of sleep apnea may or may not be made, and c) asked to notify study staff if they obtain treatment, unless treatment is obtained after their month 12 visit. Participants will be reminded that data collected as part of this study are for research purposes only and may not constitute a diagnosis of sleep apnea.

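### Section 10.2 promises a treatment covariate, while 4.2 and 10.5 specify t-tests for the same comparison; the AHI visit that defines sleep apnea is not named, and the covariate as described would probably change the contrast in 10.1

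*Combined protocol and SAP*

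**What the plan says.** - **Hypothesis (10.1):** "We hypothesize that participants with sleep apnea will have a greater 12-month change in their Montreal Cognitive Assessment scores than those without". This compares apnea with no apnea and does not mention treatment.
- **Analysis (4.2, repeated in 10.5):** "We will relate the presence of sleep apnea to change in MoCA scores between baseline and 12 months using t-tests". Mediation analyses on heart rate follow. Neither section mentions treatment or a covariate.
- **Treatment (10.2):** treatment is called a possible source of noise in the cognitive outcome, and "we will adjust for this statistically by collecting information on treatment and adjusting as a covariate". Model, coding and timing are not given.
- **Exposure (3.1):** "We will measure sleep apnea at baseline and 12 months later and relate this to cognitive function at the same time points". Sections 4.2 and 10.5 define sleep apnea as AHI of 15 or more without naming the visit. Section 7.3 speaks of either time point, but only to decide who receives a notification call.
- **Collection of treatment data (7.3):** participants called because of an AHI of 15 or more are "asked to notify study staff if they obtain treatment, unless treatment is obtained after their month 12 visit". No other route is described. On the parent CTU platform, 4.1 says "These sub-studies are able to share CTU resources for recruitment and outcome ascertainment", without saying whether apnea treatment is recorded there.

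**The concern.** An analyst who follows 10.5 drops the adjustment promised in 10.2. An analyst who follows 10.2 cannot use the test named in 10.5. Nothing ranks the two or labels one as secondary, so the choice could be made after the data are seen. A participant whose AHI crosses 15 between the visits has no defined group.

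The choice also affects what is estimated. Treatment starts after baseline and is asked about mainly in one group. A covariate of that kind does not act as ordinary adjustment for noise: it can move the comparison from all participants with apnea to those who stayed untreated. That subgroup is selected on something that happens during follow-up and may be related to severity or to expected decline.

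**Working it through.** **1. The stated power.** Section 10.2 gives about 30% with apnea (210 participants), a difference of about 0.5 points and 86% power. It gives no SD, alpha or sidedness, so 86% cannot be reproduced directly. 210 / 0.30 = 700, so I take 210 vs 490.

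Assume SD 2.0 and two-sided alpha 0.05:
- SE = 2.0 × √(1/210 + 1/490) = 0.165
- noncentrality = 0.5 / 0.165 = 3.03
- power (noncentral t, 698 df) = 85.7%

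Solving for exactly 86% gives SD 1.99 (210 vs 490) or 2.02 (210 vs 540, the full 750). The figure is therefore plausible for an unadjusted two-group comparison with SD about 2 and nobody treated.

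**2. What the covariate does.** Let A = 1 for apnea and T = 1 for treated, and fit change = b0 + b1·A + b2·T. If T = 0 in every comparator, there are three groups and three parameters:
- comparator mean = b0
- untreated apnea mean = b0 + b1
- treated apnea mean = b0 + b1 + b2

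So b1 is the untreated apnea mean minus the comparator mean. Treated cases affect only b2 and the residual variance. A least-squares check with 20%, 40% and 60% of cases treated confirmed this: b1 equalled that difference, and did not move when every treated case's outcome was raised by 1 point.

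**3. When T is zero in comparators.** This needs two conditions: baseline AHI defines the groups, and T comes only from the 7.3 call. Under both, a comparator can be asked only if called after a Month 12 AHI of 15 or more. Treatment started as a result of that call falls after Month 12 and is excluded. Treatment begun through usual care during the year could still be mentioned, so T is zero or nearly so.

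If Month 12 AHI defined the groups instead, a treated participant whose AHI had fallen below 15 would count as a comparator.

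**4. Power for untreated apnea vs no apnea.** Illustration: SD 2.0, two-sided 0.05, true untreated difference 0.5, uptake unrelated to severity, 697 residual df. Untreated n = 210 × (1 − f), where f is the share of cases treated. The documents give no value for f.

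| f | untreated n | SE | power |
|---|---|---|---|
| 5% | 199.5 | 0.168 | 84% |
| 10% | 189 | 0.171 | 83% |
| 20% | 168 | 0.179 | 80% |
| 40% | 126 | 0.200 | 71% |
| 60% | 84 | 0.236 | 56% |

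**5. If uptake is related to decline.** Suppose the overall difference is 0.5, treatment has no effect, and treated cases have twice the excess decline u of untreated cases. Then (1 − f)u + f·2u = 0.5, so u = 0.5 / (1 + f).

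| f | untreated difference | power |
|---|---|---|
| 10% | 0.45 | 76% |
| 20% | 0.42 | 64% |
| 40% | 0.36 | 43% |

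Here the covariate understates an apnea difference that is truly 0.5.

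**6. The contrast regardless of treatment.** All 210 cases stay in, but the difference shrinks if treatment works. If treatment halves the excess decline, the difference is 0.5 × (1 − f/2): 0.45, 0.40 and 0.35 at f = 20%, 40% and 60%, with power 78%, 68% and 56%. If treatment does nothing, power stays at 86%. Neither contrast has a general power advantage.

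**The case against.** Several points on the other side stand.

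- **The t-test is not wrong in itself.** A reader might infer that it must be replaced or that the primary analysis cannot be run. Neither follows. Once a visit is named, the t-test answers 10.1 for apnea regardless of treatment, and it is the same as a regression of change on apnea status alone with equal variances.
- **Missing comparator data are probable, not certain.** A reader might infer that treatment in comparators is never recorded. Section 7.3 leaves room for a comparator called at Month 12 to report earlier treatment, 10.2 promises collection without limiting it to one group, and CTU may hold the information. The route is under-described rather than shown to be one-sided.
- **The stated power is not shown to be seriously wrong.** Under 7.3, participants are only encouraged to see a family physician, and treatment must start before Month 12, so uptake may be low. At 5% to 10% treated the loss in step 4 is about 1 to 3 points.
- **The Protocol Summary adds no conflict.** It says "We will relate presence of sleep apnea to 1-year change in cognition measured using the Montreal Cognitive Assessment (MoCA" and names no test, so its silence on adjustment proves nothing.

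It could also be said that baseline classification is the natural reading and the covariate model is meant as a supporting analysis. Both are reasonable guesses, but no section states either, and 10.2 describes the adjustment without calling it secondary.

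**Conclusion.** The concern holds in a limited form, and the plan should be corrected. Two findings rest on the text alone: the covariate in 10.2 conflicts with the t-tests in 4.2 and 10.5, and the AHI visit that defines apnea is not named.

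The third finding is conditional. With baseline classification and yes/no coding from the 7.3 call, the adjusted coefficient estimates untreated apnea vs no apnea. That is a different quantity from 10.1, in a group selected after baseline, and the adjustment does not remove noise as 10.2 supposes.

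The power figures are illustrations only, resting on an assumed SD, alpha, sidedness and treated share. The table in step 4 also assumes that uptake is unrelated to severity; step 5 shows lower power when it is not. The main issue is which quantity is estimated, more than loss of power. The study remains repairable.

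**What to change.** - **4.2 and 10.5:** classify sleep apnea by baseline AHI. Name one primary analysis of 12-month MoCA change that matches 10.1, namely apnea regardless of later treatment, by the existing t-test or the equivalent regression.
- **10.2:** replace the sentence on noise and covariate adjustment with a named sensitivity analysis for treatment, with its coding and timing stated. Add a caution that the untreated-apnea contrast can be biased if uptake is related to severity or expected decline.
- **Alternative:** if the sponsor wants untreated apnea as the primary contrast, replace the t-test with the regression and reword 10.1 to match.
- **Data collection:** ask all participants at the existing Baseline and Month 12 contacts whether and when apnea treatment was started. Those already past Baseline can be asked at Month 12. If CTU already holds this, cite the source instead.

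**Cost:** a protocol amendment, which under 13.2 needs ethics board approval before it is implemented; a new case report form field; and one question at existing contacts. The stated power may become slightly less favourable once treatment is allowed for. Treatment that is not asked about during follow-up may be hard to recover later, so the question should be added early.

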### **10.3 Planned Interim Analyses**

We do not plan any interim analyses.

### **10.4 Stopping Rules**

This study will be stopped prior to its completion if: (1) the intervention is associated with adverse events that call into question the safety of the intervention; (2) difficulty in study recruitment or retention will significantly impact the ability to evaluate the study endpoints; (3) any new information becomes available during the trial that necessitates stopping the trial; or (4) other situations occur that might warrant stopping the trial.

